1.2.3 Residual Effect Period

Based on an effective half-life of 50 to 70 h the Residual Effect Period (REP) of BI 1358894 is 14 days. The Residual Effect Period (REP) of bupropion is 5 days. This is the period after the last dose with measurable drug levels and/or pharmacodynamic effects is still likely to be present.

1.3 RATIONALE FOR PERFORMING THE TRIAL

Based on in vitro data, BI 1358894 is a potential inducer of CYP2B6 at anticipated human therapeutic exposure levels. However, the predictive value of in vitro data is limited, and the probability of DDIs can be entirely assessed only with in vivo data in humans. Therefore, this trial is aimed to investigate the influence of BI 1358894 on the activity of CYP2B6 by using drug recommended by both the FDA [[P12-05791](#)] and EMA [[P15-06991](#)] as in vivo probes. Results of this DDI trial will provide a general signal of potentially important DDI upon which further exploration can be based.

1.4 BENEFIT - RISK ASSESSMENT

Participation in this clinical trial is without any (therapeutic) benefit for healthy subjects. Their participation, however, is of major importance for the development of BI 1358894. The assessment of the drug-drug-interaction (DDI) potential of BI 1358894 will contribute to a safe clinical use of this TRPC 4/5-inhibitor in patients with MDD or BPD that often have to use multiple co-medications.

Subjects are exposed to risks of study procedures and risks related to the exposure to the trial medication.

Procedure-related risks

The use of an indwelling venous catheter or venepuncture for e.g. blood sampling may result in mild bruising, and in rare cases, in transient inflammation of the wall of the vein, or nerve injury, potentially resulting in paraesthesia, reduced sensibility, and/or pain for an indefinite period.

The total volume of blood withdrawn per subject during the entire study will not exceed the volume of a normal blood donation (500 mL). No health-related risk to healthy subjects is expected from withdrawal of this volume of blood.

Drug-related risks and safety measures

In a comprehensive package of safety pharmacology, genetic toxicology, general toxicology,

Proprietary confidential information © 2021 Boehringer Ingelheim International GmbH or one or more of its affiliated companies

and nonclinical studies, BI 1358894 was demonstrated to be safe in humans for up to 13 weeks. Based on the mode of action, the pharmacological target, non-clinical toxicology data and clinical data, BI 1358894 is not considered a high risk compound for clinical studies. The single and multiple dose administrations of up to 200 mg BI 1358894 under fasted and fed conditions has been well tolerated by healthy subjects.

For details on treatment related risks, refer to CTP section [1.2](#) and the IB, version 6 [[c10354149](#)].

While there are no precedent clinical data implicating association between TRPC4/5 antagonism and Suicidal Ideation and Behavior (SIB), in the interest of ensuring participant safety, trial participants will be proactively screened and monitored for SIB in accordance with available regulatory guidance.

Because psychoactive drugs may impair thinking, judgment, and/or motor skills, participants should be cautioned about operating machinery, including automobiles, until they are reasonably certain that the study medication does not adversely affect their ability to engage in such activities. It is recommended that participants should exercise caution when driving or operating machinery.

Participants will be closely monitored during the trial participation (including safety laboratory, AE monitoring, physical and neurological examinations) to ensure that any occurring events are detected and any necessary actions taken.

BI 1358894 is a highly specific inhibitor of TRPC 4/5 channels, which are predominantly located in the CNS. All investigation into distribution and function of TRPC 4/5 (preclinical and clinical) so far have not identified any interference with the immune system, the respiratory system or the cardio-vascular system.

Therefore, no undue risk is expected from the multiple dose administration of 100 mg BI 1358894 over 19 days to healthy subjects planned for this trial.

Risks related to bupropion administration

The dose of bupropion administered in the current trial (two single doses of 150 mg extended release tablets separated by a bupropion free interval of 21 days) corresponds to the starting dose given in therapy. AEs will be appropriately monitored and could be adequately treated if necessary because the subjects will be hospitalized at the trial site under close medical surveillance for 24 h after bupropion administration. Subjects with contraindications for the use of bupropion will be excluded from participation (see Section [3](#)).

Single doses of 150 mg bupropion have been well tolerated by healthy volunteers in previous DDI trials. Due to the supposed CYP2B6 induction mediated by BI 1358894, plasma concentrations of bupropion and its metabolites may be decreased. Thus no undue risk is expected to healthy subjects from the combined administration of BI 1358894 and bupropion in this trial.

Although rare, a potential for drug-induced liver injury (DILI) is under constant surveillance by sponsors and regulators. Therefore, this trial requires timely detection, evaluation, and follow-up of laboratory alterations in selected liver laboratory parameters to ensure subjects' safety; see also section [5.2.6.1.4](#), adverse events of special interest.

Proprietary confidential information © 2021 Boehringer Ingelheim International GmbH or one or more of its affiliated companies

If the investigator should have any clinical concern, the safety of subjects will be of upmost importance. The Investigator has the discretion to remove subjects from the trial should there be any safety concerns, or if the subjects wellbeing is at jeopardy.

Taken together, the risk of study participation is considered to be minimal and justified when compared to the potential benefit of a successful clinical development of BI 1358894 for patients with MDD and BPD.

2. TRIAL OBJECTIVES AND ENDPOINTS

2.1 MAIN OBJECTIVES, PRIMARY AND SECONDARY ENDPOINTS

2.1.1 Main objectives

The main objective of this trial is to investigate the relative bioavailability of a single dose of bupropion when given alone (Reference) compared with co-administration (Test) on the 15th day of a 19-day treatment with BI 1358894 (100 mg once daily) following oral administration in healthy volunteers.

The assessment of safety and tolerability will be additional objectives of this trial.

2.1.2 Primary endpoints

[figure not shown]
The following pharmacokinetic parameters will be determined for bupropion when administered alone and co-administered at BI 1358894 steady state:

[figure not shown]
- AUC_{0-tz} (area under the concentration-time curve of the analyte in plasma over the time interval from 0 to the last quantifiable data point)
- C_{max} (maximum measured concentration of the analyte in plasma)

2.1.3 Secondary endpoint

The following pharmacokinetic parameter will be determined for bupropion when administered alone and co-administered at BI 1358894 steady state:

- $AUC_{0-\infty}$ (area under the concentration-time curve of the analyte in plasma over the time interval from 0 to infinity)

2.2.1.2 Safety and tolerability

Safety and tolerability of BI 1358894 and bupropion will be assessed based on:

- Adverse events (including clinically relevant findings from the physical/neurological examination)
- Safety laboratory tests
- 12-lead ECG
- Vital signs (blood pressure, pulse rate)
- Suicidality assessment (C-SSRS)

3. DESCRIPTION OF DESIGN AND TRIAL POPULATION

3.1 OVERALL TRIAL DESIGN AND PLAN

The trial is designed to assess effects of BI 1358894 on CYP2B6 activity after achievement of steady-state concentrations of BI 1358894.

The trial will be performed as an open-label, two period fixed sequence trial in healthy male and female volunteers enrolled at a single site. Eighteen subjects will receive the following oral treatments (for details refer to Section [4.1](#)):

- 150 mg bupropion hydrochloride as single dose on Day 1 of Visits 2 and 3
- 100 mg BI 1358894 as daily doses over 19 days from Day -14 to Day 5 of Visit 3

There will be an interval of 21 days between the single-dose administrations of the CYP2B6 probe, bupropion (Day 1 of Visits 2 and 3).

An overview of all relevant trial activities is provided in the [Flow Chart](#). For visit schedule and details of trial procedures at selected visits, refer to Sections [6.1](#) and [6.2](#), respectively.

3.2 DISCUSSION OF TRIAL DESIGN, INCLUDING THE CHOICE OF CONTROL GROUP

Because of the long (50-70 hours) half-life of BI 1358894, a fixed-sequence design was selected, in which BI 1358894 is administered in the second study period only.

For relative bioavailability trials, the crossover design is preferred because of its efficiency: since each subject serves as his/her own control, the comparison between treatments is based on an intra-subject comparison, thus removing inter-subject variability from the comparison between treatments ([R94-1529](#)).

The open-label treatment is not expected to bias results, since the study endpoints are derived from measurement of plasma concentrations of the analyte, which are provided by a bioanalytical laboratory.

Dosing durations are long enough to reliably achieve steady-state drug exposures.

3.3 SELECTION OF TRIAL POPULATION

It is planned that 18 healthy male and female will enter the study. They will be recruited from the volunteers' pool of the trial site.

A log of all subjects enrolled into the trial (i.e. who have signed informed consent) will be maintained in the ISF irrespective of whether they have been treated with investigational drug or not.

3.3.1 Main diagnosis for trial entry

The study will be performed in healthy subjects.

3.3.2 Inclusion criteria

Subjects will only be included in the trial if they meet the following criteria:

1. Healthy male or female subjects according to the assessment of the investigator, as based on a complete medical history including a physical examination, vital signs (BP, PR), 12-lead ECG, and clinical laboratory tests
2. Age of 18 to 55 years (inclusive)
3. BMI of 18.5 to 29.9 kg/m² (inclusive)
4. Signed and dated written informed consent prior to admission to the study, in accordance with GCP and local legislation
5. Male subjects, or female subjects who meet any of the following criteria from at least 30 days before the first administration of trial medication until 30 days after trial completion:
 - Sexually abstinent
 - Use of adequate contraception, e.g. any of the following methods plus condom: implants, injectables, intrauterine device
 - A vasectomised sexual partner (vasectomy at least 1 year prior to enrolment)
 - Surgically sterilised (including hysterectomy)
 - Postmenopausal, defined as at least 1 year of spontaneous amenorrhea (in questionable cases a blood sample with levels of FSH above 40 U/L and estradiol below 30 ng/L is confirmatory)

3.3.3 Exclusion criteria

Subjects will not be allowed to participate, if any of the following general criteria apply:

1. Any finding in the medical examination (including safety laboratory, BP, PR or ECG) deviating from normal and assessed as clinically relevant by the investigator
2. Repeated measurement of systolic blood pressure outside the range of 90 to 140 mmHg, diastolic blood pressure outside the range of 50 to 90 mmHg, or pulse rate outside the range of 45 to 90 bpm
3. Any laboratory value outside the reference range that the investigator considers to be of clinical relevance
4. Any evidence of a concomitant disease assessed as clinically relevant by the investigator
5. Gastrointestinal, hepatic, renal, respiratory, cardiovascular, metabolic, immunological or hormonal disorders
6. Cholecystectomy or other surgery of the gastrointestinal tract that could interfere with the pharmacokinetics of the trial medication (except appendectomy or simple hernia repair)
7. Diseases of the central nervous system (including but not limited to any kind of seizures or stroke), and other relevant neurological or psychiatric disorders
8. History of relevant orthostatic hypotension, fainting spells, or blackouts
9. Chronic or relevant acute infections

Proprietary confidential information © 2021 Boehringer Ingelheim International GmbH or one or more of its affiliated companies

10. History of relevant allergy or hypersensitivity (including allergy to the trial medication or its excipients)
11. Use of drugs within 30 days of planned administration of trial medication that might reasonably influence the results of the trial (including drugs that cause QT/QTc interval prolongation, or vaccination of any kind requiring re-vaccination during the course of the trial)
12. Intake of an investigational drug in another clinical trial within 60 days of planned administration of investigational drug in the current trial, or concurrent participation in another clinical trial in which investigational drug is administered
13. Smoker (more than 10 cigarettes or 3 cigars or 3 pipes per day)
14. Inability to refrain from smoking on specified trial days
15. Alcohol abuse (consumption of more than 12 g per day for females and 24 g per day for males)
16. Drug abuse or positive drug screening
17. Blood donation of more than 100 mL within 30 days of planned administration of trial medication or intended blood donation during the trial
18. Intention to perform excessive physical activities within one week prior to the administration of trial medication or during the trial
19. Inability to comply with the dietary regimen of the trial site
20. A marked baseline prolongation of QT/QTc interval (such as QTc intervals that are repeatedly greater than 450 ms in males or repeatedly greater than 470 ms in females) or any other relevant ECG finding at screening
21. A history of additional risk factors for *Torsade de Pointes* (such as heart failure, hypokalaemia, or family history of Long QT Syndrome)
22. Subject is assessed as unsuitable for inclusion by the investigator, for instance, because the subject is not considered able to understand and comply with study requirements, or has a condition that would not allow safe participation in the study

Female subjects will not be allowed to participate, if any of the following apply:

23. Positive pregnancy test
24. Lactation

In addition, the following trial-specific exclusion criteria apply:

25. A history of cerebral seizure
26. A history of bipolar mood disorder, bulimia or anorexia
27. Any lifetime history of suicidal behaviour (i.e. actual attempt, interrupted attempt, aborted attempt, or preparatory acts or behaviour)
28. Any suicidal ideation of type 2 to 5 on the C-SSRS in the past 12 months (i.e. active suicidal thought, active suicidal thought with method, active suicidal thought with intent but without specific plan, or active suicidal thought with plan and intent)

For study restrictions, refer to Section [4.2.2](#).

3.3.4 Withdrawal of subjects from treatment or assessments

Subjects may discontinue trial treatment or withdraw consent to trial participation as a whole ('withdrawal of consent') with very different implications; please see sections [3.3.4.1](#) and [3.3.4.2](#) below.

If a subject is removed from or withdraws from the trial prior to the first administration of trial medication, the data of this subject will not be entered in the case report form (CRF) and will not be reported in the clinical trial report (CTR). If a subject is removed from or withdraws from the trial after the first administration of trial medication, this will be documented and the reason for discontinuation must be recorded in the CRF; in addition, the data will be included in the CRF and will be reported in the CTR. At the time of discontinuation, a complete end of trial examination will be performed, if possible, and the information will be recorded in the CRF. If the discontinuation occurs before the end of the REP (see Section [1.2.3](#)), the discontinued subject should if possible be questioned for AEs and concomitant therapies at or after the end of the REP in order to ensure collection of AEs and concomitant therapies throughout the REP, if not contrary to any consent withdrawal of the subject.

3.3.4.1 Discontinuation of trial treatment

An individual subject will discontinue trial treatment if:

- The subject wants to discontinue trial treatment, without the need to justify the decision
- The subject has repeatedly shown to be non-compliant with important trial procedures and, in the opinion of both, the investigator and sponsor representative, is not willing or able to adhere to the trial requirements in the future.
- The subject needs to take concomitant medication that interferes with the investigational medicinal product or other trial treatment
- The subject can no longer receive trial treatment for medical reasons (such as surgery, adverse events [AEs], or diseases). The subject will discontinue trial treatment if he or she shows one drug-related adverse event of severe intensity or one drug-related serious adverse event.
- The subject has an elevation of AST and/or ALT ≥ 3 -fold ULN and an elevation of total bilirubin ≥ 2 -fold ULN (measured in the same blood sample) and/or needs to be followed up according to the DILI checklist provided in the ISF
- In addition to these criteria, the investigator may discontinue subjects at any time based on his or her clinical judgment.

Even if the trial treatment is discontinued, the subject remains in the trial and, given his/her agreement, will undergo the procedures for early treatment discontinuation and follow up as outlined in the [Flow Chart](#) and section [6.2.3](#).

3.3.4.2 Withdrawal of consent to trial participation

Subjects may withdraw their consent to trial participation at any time without the need to justify the decision. If a subject wants to withdraw consent, the investigator should be

Proprietary confidential information © 2021 Boehringer Ingelheim International GmbH or one or more of its affiliated companies

involved in the discussion with the subject and explain the difference between trial treatment discontinuation and withdrawal of consent to trial participation, as well as explain the options for continued follow up after trial treatment discontinuation, please see section [3.3.4.1](#) above

3.3.4.3 Discontinuation of the trial by the sponsor

Boehringer Ingelheim reserves the right to discontinue the trial at any time for any of the following reasons:

- Failure to meet expected enrolment goals overall or at a particular trial site
- New toxicological findings, serious adverse events, or any safety information invalidating the earlier positive benefit-risk-assessment. More specifically, the trial will be terminated if more than 50% of the subjects have drug-related and clinically relevant adverse events of moderate or severe intensity, or if at least 1 drug-related serious adverse event is reported
- Violation of GCP, or the CTP, or the contract with BI impairing the appropriate conduct of the trial-
- The sponsor decides to discontinue the further development of the investigational product
The investigator / trial site will be reimbursed for reasonable expenses incurred in case of trial termination (except if item 3 applies).

3.3.5 Replacement of subjects

In case more than 2 subjects do not complete the trial the Clinical Trial Leader together with the Trial Pharmacokineticist and the Trial Statistician are to decide, if and how many subjects will be replaced. A replacement subject will be assigned a unique trial subject number, and will be assigned to the same treatment as the subject he or she replaces.

4. TREATMENTS

4.1 INVESTIGATIONAL TREATMENTS

4.1.1 Identity of the Investigational Medicinal Products

The characteristics of the test product are given below:

Product 1:

Substance: BI 1358894

Pharmaceutical formulation: Film coated tablet

Source: BI Pharma GmbH & Co. KG, Germany

Unit strength: 50 mg

Posology: 2-0-0

Route of administration: oral

Duration of use: Multiple doses from Day -14 to Day 5 of Visit 3 (19 days in total)

The characteristics of the reference product are given below:

Name: Elontril

Substance: Bupropion hydrochloride

Pharmaceutical formulation: Tablet

Source: [REDACTED]

Unit strength: 150 mg

Posology: 1-0-0

Route of administration: oral

Duration of use: Single doses on Days 1 of Visit 2 and Visit 3

Bupropion will be obtained from a public pharmacy.

4.1.2 Selection of doses in the trial

In this trial, multiple daily doses of 100 mg of BI 1358894 are planned, and are considered to be safe for administration to healthy subjects. Doses of 100 mg are on the upper end of the expected efficacious dose-range likely to be used in clinical practice.

Proprietary confidential information © 2021 Boehringer Ingelheim International GmbH or one or more of its affiliated companies

The doses of bupropion are standard clinical doses. Single doses of 150 mg have been used in previous DDI trials with healthy volunteers [[P10-12978](#), [U07-1865](#), [c03050404](#)].

4.1.3 Method of assigning subjects to treatment groups

There is only one treatment sequence investigated in this trial, and each subject will be allocated to the same treatment sequence (R-T). The subjects will be allocated to a study subject number by first come first serve prior to first administration of trial medication in the morning of Day 1 of Visit 2. Once a subject number has been assigned, it cannot be reassigned to any other subject.

4.1.4 Drug assignment and administration of doses for each subject

This is an open-label, two-period, fixed-sequence trial. All subjects will receive the 2 treatments in fixed order. The treatments to be evaluated are outlined in Table [4.1.4: 1](#) below.

Table 4.1.4: 1 Dosage and treatment schedule

| Treatment | Substance | Formulation | Unit strength | Dosage | Total dose |
|---------------|-------------------------|-------------|---------------|---|------------|
| T (Test) | BI 1358894 ¹ | Tablet | 50 mg | 2 tablets (100 mg) doses on days-14 to Day 5 (19 days) of Visit 3 | 1900 mg |
| | Bupropion ¹ | Tablet | 150 mg | 1 tablet (150 mg) single dose on day 1 Visit 3 | 150 mg |
| R (Reference) | Bupropion ¹ | Tablet | 150 mg | 1 tablet (150 mg) single dose on day 1 Visit 2 | 150 mg |

¹ Drug administration after a standard continental breakfast

The trial medications will be administered to the subjects as an oral dose together with about 240 mL of water under supervision of the investigating physician or an authorised designee. Administration of BI 1358894 will be performed in the morning of Days -14 to day 5 of Visit 3, and administration of Bupropion will be performed on Days 1 of Visits 2 and 3 following a standard continental breakfast.

The consumption of the continental breakfast should occur within 30 minutes prior to dosing. PK blood samples should be taken before the study drug administration, whereas the safety laboratory samples should be taken as the first morning sample after an overnight fast.

To ensure a dosing interval of 24 hours (treatment T, Visit 3), the administration of BI 1358894 should take place at the same time every day. For BI 1358894 administration on Days -1 and 2, a deviation of no more than +/-15 min is allowed, whereas on ambulatory visits, a deviation of no more than +/- 60 min is allowed. The first BI 1358894 administration will be followed by a 2-hour post administration in-house observation period.

Proprietary confidential information © 2021 Boehringer Ingelheim International GmbH or one or more of its affiliated companies

Table 4.1.4: 2 Composition of the standard continental breakfast as an example

| Ingredients | kcal |
|--|------|
| 1 bread roll | 164 |
| 15 g butter | 113 |
| 1 slice of Gouda cheese (approximately 40g) | 146 |
| 1 slice of meat (approximately 20g) | 33 |
| 1 cup of decaffeinated coffee or tea (without sugar) | 2 |
| Sum ¹ | 458 |

¹ The total caloric content is supplied approximately as following: approx. 88 kcal as protein, approx. 133 kcal as carbohydrate, and approx. 237 kcal as fat.

Subjects will be kept under close medical surveillance until 24 h following drug administration of Bupropion. During the first 5 h after Bupropion administration, they are not allowed to lie down (i.e. no declination of the upper body of more than 45 degrees from upright posture).

The single dose Bupropion in Period Reference and the single dose of Bupropion in Period Test are to be separated by a washout period of at least 7 days. There will be 14 days follow-up period after the last BI 1358894 administration.

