1.2.2 Bupropion

Potential inductive effects of BI 1358894 on CYP2B6 will be investigated using the probe substrate bupropion.

Bupropion is used as antidepressant and smoking cessation aid. It acts as selective inhibitor of neuronal reuptake of noradrenalin and dopamine. The mechanism by which it helps in smoking cessation is unknown.

After oral administration of a 150 mg bupropion extended release tablet (as used in this trial), t_{max} was observed at approximately 2.5-3 h. Bupropion is extensively metabolised with only 0.5% excreted unchanged in either faeces or urine. Hydroxybupropion, threohydrobupropion and erythrohydrobupropion are active metabolites. Only the formation of hydroxybupropion is catalysed via CYP2B6.

Based on a mouse antitetrabenazine model, hydroxybupropion is approximately 50% as active as bupropion, and threohydrobupropion and erythrohydrobupropion are approximately 20% as active as bupropion [[P06-00643](#)]. Plasma Cmax and AUC of the main metabolite hydroxybupropion are approximately 3- and 14-fold higher than for bupropion, respectively. t_{max} of hydroxybupropion is reached approximately 6 h after administration of a single dose of bupropion [[R21-0979](#)].

Clinically, bupropion is used as a racemate, and disposition is stereoselective. CYP2B6 catalyzes hydroxylation of both enantiomers, R-bupropion and S-bupropion, to R,R-hydroxybupropion and S,S-hydroxybupropion, respectively. The rate of S-bupropion hydroxylation has been reported to exceed R-bupropion hydroxylation by approximately 1.5- to 3-fold. Interestingly, S,S-hydroxybupropion plasma concentration is formation-rate limited, whereas R,R-hydroxybupropion is elimination-rate limited [[R14-3843](#)]. Therefore, both plasma concentration of S,S-hydroxybupropion and the metabolite-to-parent ratio of S,S-hydroxybupropion to S-bupropion may be used as parameters for CYP2B6 activity in addition to plasma concentrations of bupropion or S-bupropion.

Mean plasma $t_{1/2}$ of bupropion, hydroxybupropion, threohydrobupropion, and erythrohydrobupropion is approximately 20, 20, 37, and 33 h, respectively [[R21-0979](#)].

Maximal daily dose of bupropion is 300 mg. Recommended treatment duration is 7-9 weeks for smoking cessation or >6 months for treatment of depression.

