6.2.2 Treatment periods

Each subject is expected to participate in 2 treatment periods (Days 1 to 6 in period 1, day -14 to 6 in period 2). At least 6 days will separate drug administrations in the first and second treatment periods.

Proprietary confidential information © 2021 Boehringer Ingelheim International GmbH or one or more of its affiliated companies

On Day -1 of each treatment period, study participants will be admitted to the trial site and kept under close medical surveillance for at least 24 h following drug administration. The subjects will then be allowed to leave the trial site after formal assessment and confirmation of their fitness. On all other study days, subjects will be treated in an ambulatory fashion.

For details on time points and procedures for collection of plasma samples for PK analysis, refer to [Flow Chart](#) and Section [5.3.2](#).

The safety measurements performed during the treatment period are specified in Section [5.3](#) of this protocol and in the Flow Chart. For details on times of all other trial procedures, refer to the Flow Chart. AEs and concomitant therapy will be assessed continuously from screening until the end of trial examination.

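### Do the 21-day, 7-day and 6-day intervals between the two periods conflict in a way that affects the trial?

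*Protocol*

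**What the plan says.** Four sections of the protocol deal with the spacing of the periods.

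- Section 3.1: "There will be an interval of 21 days between the single-dose administrations of the CYP2B6 probe, bupropion" (Day 1 of Visits 2 and 3).
- Section 1.4, on bupropion risk: the two doses are "separated by a bupropion free interval of 21 days".
- Section 4.1.4: the Reference dose and the "single dose of Bupropion in Period Test are to be separated by a washout period of at least 7 days".
- Section 6.2.2: "At least 6 days will separate drug administrations in the first and second treatment periods". The doses are not named, but the sentence before it defines the periods as "Days 1 to 6 in period 1, day -14 to 6 in period 2".

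The BI 1358894 schedule in section 3.1 is "100 mg BI 1358894 as daily doses over 19 days from Day -14 to Day 5 of Visit 3". The Period T Flow Chart places its first dose at -336:00 relative to Test bupropion.

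**The concern.** Sections 3.1 and 4.1.4 speak of the same two bupropion doses, yet one gives 21 days and the other at least 7. Taken alone, a 7-day gap would start BI 1358894 a week before the Reference dose. The Reference profile would then no longer be free of the perpetrator drug, and the test/reference ratio would lose its meaning. Section 6.2.2 adds a third figure which, counted dose to dose, leads to 20 days.

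The two Flow Charts number their days separately. SAP 6.7 refers to protocol 6.1 for time windows, and 6.1 gives none for the gap between periods. It is therefore reasonable to ask whether the site knows when Period T starts, and whether the Report Planning Meeting could say if a 20-day interval is a deviation.

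**Working it through.** **Inputs.** Run-in of BI 1358894 before Test bupropion: 336 h / 24 = 14 days (Flow Chart, Period T). Last Reference sample: 120 h = 5 days (Flow Chart, Period R). Half-lives of bupropion and its hydroxy-, threohydro- and erythrohydro- metabolites (protocol 1.2.2): "is approximately 20, 20, 37, and 33 h, respectively".

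**The plan's own figure.** Bupropion-to-bupropion interval = (Reference bupropion to first BI 1358894) + 14.

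- 7 + 14 = 21 days, the figure in 3.1 and 1.4.
- 6 + 14 = 20 days, if the 6 days of 6.2.2 are counted dose to dose.
- If 6.2.2 means six dose-free days, BI 1358894 starts on the seventh day after bupropion, and 7 + 14 = 21 days again.

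**Can one schedule meet all the statements?** Take 21 days between the bupropion doses, so that the first BI 1358894 dose comes 21 - 14 = 7 days after Reference bupropion.

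| Section | Requirement | 21-day schedule |
|---|---|---|
| 3.1, 1.4 | 21 days, bupropion to bupropion | 21 = 21 |
| 4.1.4 | at least 7 days, bupropion to bupropion | 21 ≥ 7 |
| 6.2.2 | at least 6 days, between the periods' drug administrations | 7 ≥ 6 |

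All are met. The 7-day minimum in 4.1.4 is not violated; it simply does not bind.

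**Are the harmful schedules allowed?**

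- BI 1358894 on or before the Reference dose needs an interval of 14 days or less (7 - 14 = -7; 14 - 14 = 0). Section 3.2 confines BI 1358894 to the second period, and 4.1.3 fixes the order as R then T.
- BI 1358894 before the 120 h Reference sample needs an interval under 5 + 14 = 19 days. Section 6.2.2 excludes this, because 6 days exceeds 5. SAP Table 6.1: 1 also places a bupropion follow-up phase, starting 5 days after the dose, before the first BI 1358894 dose.

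**Carry-over.** Residual fraction = 2^(-24 × days / half-life), assuming first-order decline.

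| Interval | Bupropion (20 h) | Erythrohydrobupropion (33 h) | Threohydrobupropion (37 h) |
|---|---|---|---|
| 7 days (cannot occur) | 8.4 half-lives, 0.30% | 2.9% | 4.3% |
| 20 days | 24 half-lives, <0.001% | 0.004% | 0.012% |
| 21 days | 25.2 half-lives, <0.001% | 0.003% | 0.008% |

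Hydroxybupropion has the same half-life as bupropion. Only bupropion itself carries the primary and secondary endpoints. For comparison, protocol 7.3 gives a predose bupropion concentration above 5% of Cmax as an example of non-evaluable data, and Period T includes a predose bupropion sample at -0:30.

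**The case for a change.** The strongest argument for a change concerns conduct. Sections 3.1 and 4.1.4 name the same pair of doses with different figures, and the lower bound in 4.1.4 cannot be reached under this design. It gives 21 days only if counted to the first BI 1358894 dose, which is not what it says. Section 6.2.2 leaves its anchor doses unnamed. No window is stated around the 21 days, so whether 20 days complies depends on how one counts. Global Amendment 2 corrected similar conflicts over dosing windows in 4.1.4 and 6.1 without needing approval, so a correction would be cheap.

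All of that is fair as a description of the text, but none of it changes what is done or concluded. A site that follows 3.1 breaches nothing, and 3.1 itself links the two day-numbering systems through Day 1 of Visits 2 and 3. A one-day difference does not touch the Test condition, because the 14-day run-in is set within Period T. If a 20-day interval arose, SAP 6.2 sends it to the Report Planning Meeting. Under protocol 7.3, data are excluded for deviations relevant to the PK evaluation or for non-evaluability. At 24 half-lives a missing day is neither. The label attached to such a case might vary; the analysed data would not.

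**Conclusion.** The concern does not hold as a fault in the design. There is one fixed interval and two minima with loose anchors, and a single schedule satisfies them all. The remaining ambiguity is at most 20 against 21 days, with residual bupropion below 0.001% either way, so the estimated ratios and their confidence intervals are unaffected.

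This rests on three assumptions:

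- the sections are read together, so that a loose minimum does not cancel an explicit interval;
- 1.4 counts from dose to dose, as 3.1 does, and the Period 2 drug administrations in 6.2.2 begin with BI 1358894 on Day -14;
- bupropion declines at roughly the stated half-life. Section 1.2.3 agrees with this order of magnitude: "The Residual Effect Period (REP) of bupropion is 5 days".

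If these sections are revised for another reason, their wording should be reconciled, with each interval naming its start and end dose. The value is the sponsor's to set. On its own, the point is a clerical one.
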